Can adequacy of anesthesia depth and quality of recovery be influenced by the level of neuromuscular blockade?

	
 • Minimum duration of surgery is 90 minutes and performed with total intravenous anaesthesia (TIVA) with the hypnotic propofol, the analgesic remifentanil and the neuromuscular relaxant rocuronium • Patients that are able to and do provide a signed informed consent form 
Exclusion criteria
 
 • Patients with neuromuscular diseases and severe cardiac and respiratory pathologies • or that have any contra indication for any of the drugs used • or that are not able to complete the baseline PQRS test. • Indication to perform tracheal intubation using fibroscopy • Patients who are pregnant or nursing.
Sample Size	Seventy patients will be enrolled.
Duration	
1 year and 4 months divided as follows:
 
 • 4 months (from the preparation of the forms for submission to acceptance of the National Ethics Committee, National Committee for Data Protection, and National Authority of Medicines and Health Products – the estimated time for response of the National Committees is 2 months) • 8 months for patient enrolment and data collection (an average of 2 patients per week) • 2 months for finishing the database and statistical analysis

Can adequacy of anesthesia depth and quality of recovery be influenced by the level of neuromuscular blockade?

	
 • 2 months for the analysis of results and finalizing the Clinical Report Study
Primary Objective	
The objective of this study is to assess if the use of deep neuromuscular blockade reversed with sugammadex, and the consequent suppression of the EMG activity, can improve the overall stability of an anesthetic procedure (guided using BIS monitoring) and allow a reduction in the amount of anesthetic drugs required for adequate anesthesia.
 
Patients subjected to anterior cervical spine surgery under general intravenous anesthesia will be randomized to receive one of two protocols regarding the neuromuscular blockade: our institution's standard practice of non-deep rocuronium blockade or deep neuromuscular blockade reversed with sugammadex

Secondary Objectives	
As a secondary objective, we will study the quality of recovery using the PQRS scale to see if maintaining a deep NMB level during surgery has an impact on the patients' quality of recovery.

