Primary Endpoint	
Anesthetic stability, measured by the variability of the Bispectral Index of the EEG

Secondary Endpoint	
Quality of recovery using the PQRS scale

Intervention	
Deep neuromuscular blockade reversed with sugammadex.

Can adequacy of anesthesia depth and quality of recovery be influenced by the level of neuromuscular blockade?

3. Abbreviations

AE	Adverse event
ALT	Alanine transaminase
AST	Aspartate aminotransferase
BIS	Bispectral Index
CEIC	Portuguese Central Ethics Committee "Comissão de Ética para a Investigação Clínica"
CIOMS	Council for International Organizations of Medical Sciences
CNPD	Portuguese Data Privacy Agency "Comissão Nacional de Protecção de Dados"
DSUR	Development Safety Update Report
ECI	Event of Clinical Interest
eCRF	Electronic Case Report Form
EMG	Electromyography
GCP	Good Clinical Practice
IB	Investigator's Brochure
ICH	International Conference of Harmonization
IMP	Investigational Medicinal Product
Infarmed	Portuguese Regulatory Authority "Instituto da Farmácia e do Medicamento"
MAP	Mean Arterial Pressure
NIMP	Non Investigational Medicinal Product

Can adequacy of anesthesia depth and quality of recovery be influenced by the level of neuromuscular blockade?

NMB	Neuromuscular blockade
PQC	Product Quality Complaint
PQRS	Physician Quality Reporting System
PTC	Post Tetanic Count
SAE	Serious adverse event
SMP	Summary of Product Characteristics
SUSAR	Serious Unexpected Suspected Adverse Reaction
TCI	Targeted controlled infusion
TOF	Train-of-four
ULN	Upper Limit Normal

4. Background and rationale

The Bispectral Index (BIS) of the electroencephalogram (EEG) uses a four-electrode sensor placed on the forehead and is widely used as a quantifiable measure of depth of sedation and depth of anesthesia (DOA) [1-3]. Currently all DOA monitors are EEG based and use indexes similar to the BIS. Scientific evidence for the benefits of BIS guided anesthesia are abundant [4]. Insufficient anesthesia may cause Intraoperative awareness, which may be prevented by maintaining BIS values between 40 and 60 [5-7]. Excessive anesthesia, namely BIS below 45 or 40, is being increasingly associated with increased mortality at one or more years following surgery [8,9], especially if combined with hypotension [10]. Therefore, guiding anesthesia aiming at maintaining BIS within the recommended range offers important advantages. According to a recent NICE report it is also cost effective [11].

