The primary hypothesis is that there is a better anesthetic stability in the deep NMB group (Group 2) and that this is translated as a reduction of the BIS signal variability and a reduction in the required effect-site concentrations of propofol and remifentanyl (representative of the total drug consumption).

b) Secondary objectives

As a secondary objective, we will study the quality of recovery using the PQRS scale to see if maintaining a deep NMB level during surgery has an impact on the patients' quality of recovery.

The secondary hypothesis is that the quality of recovery (PQRS test) is better in the patients of Group 2.

Can adequacy of anesthesia depth and quality of recovery be influenced by the level of neuromuscular blockade?

6. Study design

Patients subjected to anterior cervical spine surgery under general intravenous anesthesia will be randomized to receive one of two protocols regarding the neuromuscular blockade:

- Group 1 – Standard Clinical Practice Group - standard NMB, with a standard rocuronium dose for intubation (0.6 mg/kg). If required, the reversal of neuromuscular block is performed with neostigmine.
- Group 2 – Deep NMB group - with a standard rocuronium dose for intubation (0.6 mg/kg), followed by a constant infusion of rocuronium (10-15 µg/kg/min) to guarantee a PTC less or equal to 2 on the TOF monitor (PTC is evaluated every 5 minutes). The reversal of neuromuscular block is performed with Sugammadex (4 mg/kg).

a) Primary Endpoints

- BIS signal variability using the measured standard deviation during the maintenance phase of anesthesia
- Required effect-site concentrations of remifentanyl and propofol

b) Secondary Endpoints

- PQRS results at 15 and 40 minutes after surgery (taking into account the patient baseline values of the PQRS test done on the pre-anesthetic visit)
- PQRS results at day 3 after surgery

c) Study type

This is an interventional, phase 4, double-arm, parallel, randomized, open-label, single-center study aiming to compare two anesthesia protocols.

Can adequacy of anesthesia depth and quality of recovery be influenced by the level of neuromuscular blockade?

d) Study Timeline

- Study Start Date: April 2016
- Study End Date: April 2017
- First Patient In: April 2016
- Last Patient In: April 2017
- Last Patient Out: April 2017
- Study Analysis: May 2017
- Publication: November 2017

Can adequacy of anesthesia depth and quality of recovery be influenced by the level of neuromuscular blockade?

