Sample size calculation with a power of 0.80 and an α of 0.05, considering the primary hypothesis of a reduction in the BIS variability (measured as the standard deviation) and a reduction in the propofol and remifentanil drug consumption (measured as the average effect-site concentration required) during maintenance of anesthesia.

To estimate the standard deviation of our population, we searched our database for standard clinical practice cases with: online data recording; cervical spine surgery; BIS average values within the recommended target values [40-60]; TCI anesthesia with propofol and remifentanil.

A total of 12 patients data were analyzed (mainly due to the lack of online recording during the procedures), the average BIS standard deviation was 8.7 ± 3.14 , and the average propofol and remifentanil effect-site concentrations were 2.68 ± 0.9 $\mu\text{g/ml}$ and 2.83 ± 0.8 ng/ml , respectively.

Can adequacy of anesthesia depth and quality of recovery be influenced by the level of neuromuscular blockade?

A 25% reduction on the BIS variability (standard deviation) was considered clinically relevant, and gave a minimum sample size of 26 per group.

A reduction on propofol average effect-site concentration of 20% was considered clinically relevant, and gave a minimum sample size of 34 per group.

A reduction on remifentanil average effect-site concentration of 20% was considered clinically relevant, and gave a minimum sample size of 24 per group.

Considering the above results and the possibility of patient exclusion due to external complications during surgery, a total of 35 patients per group will be included in the study.

The secondary variable, result of the PQRS test was not used in the sample size calculation, since there are no studies on the comparison of recovery after two different interventions and the data regarding sample calculation that the authors of PQRS showed us are for the recovery at 3 days post-surgery, which is not comparable to our study. Therefore we did not consider adequate to estimate a percentage difference for which we do not know the clinical reality.

The surrogate variables, consumption of ephedrine and labetalol will be analyzed since these drugs are used in the response protocol to target deviations, but they are not considered for the sample size calculation.

c) Level of statistical significance

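### The primary endpoint is defined in two ways with no success rule, and if all three outcomes must succeed the stated power of 0.80 is not delivered at 35 per group

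*Combined protocol and SAP*

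**What the plan says.** The documents define the primary endpoint in two ways.

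- **Synopsis, Primary Endpoint row:** "Anesthetic stability, measured by the variability of the Bispectral Index of the EEG". No drug outcome appears in this row.
- **Synopsis, Primary Objective, and section 5a:** the intervention should improve stability and also "allow a reduction in the amount of anesthetic drugs required for adequate anesthesia".
- **Section 5a, primary hypothesis:** "a reduction of the BIS signal variability and a reduction in the required effect-site concentrations of propofol and remifentanyl".
- **Section 6a, Primary Endpoints:** "BIS signal variability using the measured standard deviation during the maintenance phase of anesthesia", followed by "Required effect-site concentrations of remifentanyl and propofol".
- **Section 11b:** "Sample size calculation with a power of 0.80 and an α of 0.05, considering the primary hypothesis" of a fall in BIS variability and "a reduction in the propofol and remifentanil drug consumption". Each outcome is then sized separately, giving 26 per group for BIS, 34 for propofol ("gave a minimum sample size of 34 per group") and 24 for remifentanil. Enrolment is set at 35 per group.

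Section 11a plans independent-samples t tests for continuous data, and section 11c calls p below 0.05 significant. Section 11 gives no success rule, no testing order and no sidedness.

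**The concern.** Suppose BIS variability falls significantly and propofol concentration does not. The synopsis row supports calling the trial positive; the joint wording in sections 5a and 11b supports calling it negative. Nothing in section 11 settles the matter. The trial is open-label and a paper on the primary objective is planned, so a rule chosen after the results are known would carry little weight.

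The power statement has a related gap. The 0.80 is attached to a hypothesis with three parts, but the calculation gives 0.80 for each part on its own. If all three parts must succeed, the chance of success is lower than the chance for the weakest part, unless the other two never fail when that one succeeds.

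**Working it through.** **Inputs (section 11b; 12 standard-practice patients).** The common SD in both arms is an assumption, because the plan gives SDs for standard practice only.

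| Outcome | Mean ± SD | Reduction | δ | δ/SD | Stated n per group |
|---|---|---|---|---|---|
| BIS SD | 8.7 ± 3.14 | 25% | 2.175 | 0.693 | 26 |
| Propofol | 2.68 ± 0.9 | 20% | 0.536 | 0.596 | 34 |
| Remifentanil | 2.83 ± 0.8 | 20% | 0.566 | 0.708 | 24 |

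**Step 1: reproduce the stated n.** The normal approximation is n = 2(z_α + z_0.80)² / (δ/SD)². The squared sum is (1.645 + 0.842)² = 6.18 one-sided and (1.960 + 0.842)² = 7.85 two-sided.

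| Assumption | BIS | Propofol | Remifentanil |
|---|---|---|---|
| Stated | 26 | 34 | 24 |
| One-sided, equal raw SD | 25.8 | 34.9 | 24.7 |
| Two-sided, equal raw SD | 32.7 | 44.3 | 31.4 |
| Two-sided, SD proportional to mean | 25.6 | 36.3 | 25.7 |
| Two-sided, log scale | 23.2 | 33.7 | 24.2 |

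For SD proportional to the mean, 2·SD² becomes SD²[1 + (1 − r)²], where r is the fractional reduction. For the log scale, δ/SD becomes −ln(1 − r) / √ln(1 + CV²). For propofol, CV = 0.9/2.68 = 0.336 and the ratio is 0.223/0.327 = 0.683. Three of the four sets of assumptions come close to the stated figures, so the figures do not identify the method.

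**Step 2: power of each outcome at 35 per group.** This uses the planned t test on the raw scale with equal SDs: noncentral t, 68 degrees of freedom, noncentrality (δ/SD)√(35/2).

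| | BIS | Propofol | Remifentanil |
|---|---|---|---|
| One-sided 0.05 | 88.9% | 79.4% | 90.1% |
| Two-sided 0.05 | 81.5% | 69.0% | 83.1% |

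**Step 3: power for all three.** Whatever the correlation, this cannot exceed the smallest single power, which is 79.4% one-sided or 69.0% two-sided. Under independence the products are 0.889 × 0.794 × 0.901 = 0.64 and 0.815 × 0.690 × 0.831 = 0.47. Simulation of correlated t statistics, with an assumed common correlation, gives:

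| Correlation | 0 | 0.5 | 0.9 |
|---|---|---|---|
| One-sided | 64% | 70% | 78% |
| Two-sided | 47% | 57% | 67% |

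**Step 4: take the plan's own minima at face value.** Suppose 26, 34 and 24 each give exactly 80% one-sided. Then power at 35 is Φ(2.487√(35/n) − 1.645), which is 89% for BIS, 81% for propofol and 91% for remifentanil. The ceiling is now 81%, but the product under independence is 0.89 × 0.81 × 0.91 = 0.66. So even on the plan's own sizes, the joint hypothesis reaches 0.80 only if the three outcomes succeed almost entirely together.

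**The case against.** Section 11b sizes each outcome separately and enrols just above the largest figure. That is a coherent plan for 0.80 per endpoint, and no passage states that all three must succeed. This stands: the firm defects are the conflicting synopsis row and the missing rule, and the power shortfall follows only under the all-three reading. That reading is nevertheless the natural one, since section 11b ties the 0.80 to a hypothesis that joins the outcomes.

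The size of the shortfall depends on the model, and this also stands. One-sided, propofol misses 0.80 by 0.6 points with the t test and reaches 80.1% by the normal approximation. Two-sided on the log scale, propofol has 80.4% and all-three power is about 68–79% for correlation 0 to 0.9. One-sided log-scale testing would bring all-three power above 0.80, but the Step 1 formula then gives 18.3/26.5/19.1 per group, which is not what the plan reports, and section 11a mentions no log transformation. With 12 patients, the 95% interval for an SD (normal data) runs from 0.71 to 1.70 times its estimate, so two-sided propofol power at 35 could lie anywhere from about 93% to 30%.

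Three stronger readings are tempting, and the documents do not support them.

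- *The test must have been one-sided.* Step 1 shows two-sided assumptions that fit about as well.
- *The false-positive rate is inflated.* If all three must succeed, 0.05 each controls it. It would rise, to 1 − 0.95³ = 14% under independence, only if any single outcome sufficed, and no passage says so.
- *The synopsis leaves out the drug outcomes.* Its title, rationale and Primary Objective include them; only the Primary Endpoint row does not.

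**Conclusion.** The point holds. The Primary Endpoint row conflicts with sections 5a, 6a and 11b, and section 11 gives neither a success rule nor a sidedness. This must be settled before data are seen.

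If all three outcomes are required, 0.80 does not describe the joint hypothesis at 35 analysed per group. Joint power is about 64–78% one-sided or 47–67% two-sided. These ranges rest on the raw-scale t test, the section 11b means, SDs and effects, the same raw SD in both arms, and an assumed common correlation of 0 to 0.9, for which the documents give no value. The shortfall is smaller if the SD falls with the mean or a log scale is used. Section 11b mentions exclusions only as a possibility; any that occur would lower the figures further.

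A reader might infer that the trial is too small and must enrol more. That does not follow: an openly stated joint power below 0.80 is an acceptable choice.

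**What to change.** Before data are seen:

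1. List all three endpoints in the synopsis Primary Endpoint row, to match sections 5a, 6a and 11b.
2. State in section 11 that all three must be significant at 0.05 each, with no split of alpha, and state whether the tests are one- or two-sided.
3. In section 11b, give the formula, sidedness and SD assumption behind 26/34/24. Replace the single 0.80 with the power of each endpoint and a joint power range with its correlation assumption. The sponsor can estimate the correlation from its own 12 cases, though imprecisely.

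This edits one synopsis row and section 11 and adds no patients. Section 11f already requires that statistical changes go to the authorities before they are implemented. The cost is a stated joint power below 0.80, with propofol the likeliest to miss. Restoring 0.80 is optional and, on the Step 2 assumptions with correlation 0.9 to 0, would take about 38–46 per group one-sided or 47–56 two-sided.

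The alternative is to make BIS SD the sole primary endpoint (88.9% power one-sided or 81.5% two-sided at 35) and test the drug outcomes only after it succeeds, in a fixed order or with Holm's method. That matches the synopsis row, but it costs more: it changes sections 2, 5, 6a and 11, demotes the drug-requirement question in the trial's title, and makes every drug claim conditional on BIS.
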